Study of the Efficacy of 532nm Laser and 1064 nm Laser in the Treatment of
Cutaneous Lupus Erythematosus Versus Topical Corticosteroids Alone

NCT03639857

Date: May 22nd, 2019

1) Protocol Title

A Comparative Study of the Efficacy of 532nm Laser and 1064 nm laser as Adjuncts to Topical Corticosteroids in the Treatment of Cutaneous Lupus Erythematosus Versus Topical Corticosteroids Alone

2) Principal Investigator

[name] M.D., UCF College of Medicine, UCF Health

Co-Principal Investigator: [name] M.D., UCF Health

Co-Principal Investigator: [name] B.S., UCF College of Medicine

Co-Principal Investigator: [name] B.A., UCF College of Medicine

Co-Principal Investigator: [name], B.S., UCF College of Medicine

Co-Principal Investigator: [name], B.S., UCF College of Medicine

Sub-Investigator: [name], B.A., UCF College of Medicine

Sub-Investigator: [name], B.A., UCF College of Medicine

3) Objectives

This study aims to compare the efficacy of 532nm Potassium Titanyl Phosphate (KTP) laser and 1064 nm Neodymium-doped Yttrium Aluminum Garnet (Nd:YAG) laser as adjuncts to topical corticosteroids in the treatment of cutaneous lupus erythematosus versus topical corticosteroids alone.

Our hypothesis is that adding laser treatment to standard of care will result in quicker resolution of lesions of cutaneous lupus. Furthermore we hypothesize that the 532nm laser will be more effective than the 1064nm laser.

The results of the study will either be submitted for publication in a journal or presented at a conference. Data from this study also could be used for further studies to clarify the ideal laser settings for use in cutaneous lupus.

4) Background

Systemic Lupus Erythematosus (SLE) is an autoimmune disorder characterized by the production of autoantibodies that can affect almost every organ in the human body. Most commonly there is a skin and musculoskeletal involvement, but there also can be hematologic, renal, and central nervous system manifestations as well.¹

It is estimated that 80% of people with SLE have skin involvement referred to as Cutaneous Lupus Erythematosus (CLE). CLE can develop independently of SLE and is more prevalent than SLE alone. Women ages 20 to 50 years old are most commonly affected by CLE although males and other ages can be affected as well.²

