 - Unable to read and speak English since consent will only be available in English

[figure not shown]
- d) Study Endpoints
 - Primary endpoints: Participation in the study will end after the third visit.
 - Primary safety endpoints: none
 - Secondary safety endpoints:
 - Adverse reaction to the laser treatment such as blister, ulceration, and scarring.
 - Adverse reaction to the topical steroid such as atrophy, telangiectasias or striae.
 - Intolerance to pain of laser procedure.

- e) Study Timelines
 - Each participant will be in the study for a maximum of 8 weeks. Participants will receive 2 laser treatments. The laser treatments will be spaced 4 weeks apart between visit 1 and visit 2. Finally, 4 weeks after visit 2, the participants will be followed up during visit 3.

 - The duration expected for all study participants to be recruited is estimated to be 28 weeks.

 - The study will end when the last participant has completed the 2 laser treatments and follow up. The goal is to conclude the data collection by October 31, 2018 and complete primary analysis by December 31, 2018.

- f) Procedures involved in the Human Research.
- This study will be a randomized prospective study. All study lesions will receive topical treatment. One lesion will only receive topical treatment to serve as a control, and up to 2 others will also receive laser treatment in addition to the topical treatment.
 - Standard of care treatment will be a topical corticosteroid as follows:
 - Discoid lupus lesions: Betamethasone dipropionate augmented 0.05% cream twice a day as needed
 - Non-discoid cutaneous lupus lesions: Triamcinolone acetonide 0.1% cream twice a day as needed
 - Laser treatment will be randomized based upon the participant Fitzpatrick Skin Type as follows:
 - Fitzpatrick Skin Types I – III:
 - § Treatment lesion will be treated with 532nm laser or 1064nm laser
 - § 50:50 randomization for laser used (determined by coin flip)
 - § If the participants have an additional lesion then this will be treated with the laser not used for the treatment lesion
 - Fitzpatrick Skin Types IV - VI
 - § Treatment lesion will only be treated with the 1064nm laser. This is because the 532 nm wavelength is absorbed easily by melanin and thus can cause skin pigmentation abnormalities when used with darker skin participants.
 - Laser treatment system details and parameters:

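### Section 7(f) describes a coin flip for laser wavelength but no random draw of which lesion is the topical-only control, so the title comparison may not be randomised

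*Combined protocol and SAP*

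**What the plan says.** Section 3 gives the first hypothesis as "adding laser treatment to standard of care will result in quicker resolution of lesions of cutaneous lupus". Section 7(f) labels the design: "This study will be a randomized prospective study". It then sets the lesion roles: "One lesion will only receive topical treatment to serve as a control, and up to 2 others will also receive laser treatment". No rule follows for which lesion becomes the control.

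The allocation text opens with "Laser treatment will be randomized based upon the participant Fitzpatrick Skin Type as follows". Under that heading:

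- **Skin types I–III:** the treatment lesion gets one of the two wavelengths, by "50:50 randomization for laser used (determined by coin flip". For a further lesion, "If the participants have an additional lesion then this will be treated with the laser not used for the treatment lesion".
- **Skin types IV–VI:** "Treatment lesion will only be treated with the 1064nm laser". No random step is described.

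The Visit 1 entry in the 7(f) timeline places baseline assessment first, then lesion selection, then randomisation, then the first treatment. It does not say what is randomised. Section 7(c) requires at least two active lesions per participant.

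**The concern.** Laser against topical alone is the main comparison of the trial, and it is made between lesions of the same participant. The coin has two outcomes, 532nm and 1064nm, and neither is control. It acts on a lesion that already carries the label of treatment lesion. In a participant with only two lesions, the undescribed step is the whole of the laser–control allocation.

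Lesion selection comes after the baseline assessment, so whoever assigns roles can know the scores. For ill-defined lesions, 7(f) takes a 2 cm² area within the involved skin and does not say how it is located, which adds discretion.

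If roles follow appearance, the laser–control contrast carries selection bias. Section 7(g) names no efficacy test and no baseline adjustment. The only laser–control contrast the plan defines is the difference in change of active CLASI in the 7(h) suspension rule. That is a safety trigger, but it is a change score, and change scores are sensitive to which lesion starts worse.

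**Working it through.** **Reading the text.** The plan gives no figure on this point, so the allocation statements are compared directly.

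| Contrast | Random step described in 7(f) |
|---|---|
| 532nm v 1064nm, types I–III | Yes, coin flip; a further lesion gets the other laser |
| Laser v control, types I–III | None |
| Laser v control, types IV–VI | None |

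The wavelength contrast in types I–III is therefore validly randomised. The gap concerns laser against control only.

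**Illustrating the consequence.** From the documents: 25 participants (section 7(a)). Assumed, because the documents give no values: two independent lesions per participant, normal scores with higher meaning worse, baseline SD 1 point, no laser effect, and an unadjusted two-sided paired t-test on change at 0.05. Rates are from 100,000 simulated trials per setting.

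The expected gap between the worse and the milder of two independent normal baselines is 2/√π = 1.128 SD. If the slope of week-8 score on baseline is b, and the worse lesion is lasered with probability p, then

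bias in favour of laser = (2p − 1) × (1 − b) × 1.128.

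With equal SDs at both times, b equals the correlation. At p = 1:

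- b = 0.5: 0.5 × 1.128 = 0.564
- b = 0.7: 0.3 × 1.128 = 0.339 (0.338 with the rounded factor)
- b = 0.9: 0.1 × 1.128 = 0.113

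False findings that laser is better (nominal 2.5%):

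| Worse lesion lasered | Correlation 0.5 | 0.7 | 0.9 |
|---|---|---|---|
| 100% | 54.9% | 34.4% | 13.9% |
| 75% | 16.4% | 11.5% | 6.3% |
| 60% | 5.7% | 4.8% | 3.8% |
| 50% (random draw) | 2.5% | 2.5% | 2.5% |

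If the milder lesion is always lasered, the errors are of the same size but against laser (54.9 / 34.3 / 13.7%).

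**The direction is not fixed even when the worse lesion is lasered.** Let the week-8 SD be 1.25 times baseline, so b = 1.25 × correlation, with p = 1:

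- correlation 0.7, b = 0.875: 0.125 × 1.128 = 0.14 points for laser, false finding for laser 7.8%
- correlation 0.8, b = 1.0: no bias
- correlation 0.9, b = 1.125: 0.14 points against laser, false finding against laser 13.7%

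**Would a baseline check reveal it?** The mean baseline imbalance is (2p − 1) × 1.128, that is 1.13, 0.56 and 0.23 points at 100%, 75% and 60% selection. A paired baseline test at 0.05 detects it in 100%, about 55% and about 13% of trials (40,000 simulations). A non-significant check does not rule out milder selection.

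**Would adjustment repair it?** Regress the follow-up difference on the baseline difference and test the intercept. If selection used the recorded score alone, the bias is 0.00 and the error rate is 2.4–2.6% each way. At correlation 0.5, always-worst selection raises the standard error from 0.25 under a random draw to 0.42. If selection used anything beyond the recorded score, adjustment does not guarantee removal.

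**The case against.** No sentence says that lesions are given roles by appearance, so the harm is inferred. The documents also lean some way towards a draw. Section 7(f) calls the study randomised without limiting this to wavelength, and the split into control and laser lesions follows shortly after. The Visit 1 entry lists randomisation for all participants, and in types IV–VI, where the wavelength is fixed, lesion role is the only thing left to randomise. One figure just before section 7(d) is not legible in the text reviewed, and the attached survey form that records lesion treatment was not available; either could settle the matter. The simulated figures rest on assumed inputs, two lesions rather than up to three, and an unadjusted test that the plan does not prescribe. They run from negligible to large, in either direction.

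Most of this stands. It limits the finding to what the text fails to say and makes the figures illustrative only. It does not close the gap: neither general sentence says what is randomised, and where 7(f) spells out the procedure, it covers wavelength alone. Pairing removes differences between participants, and scores and photographs make measured imbalance checkable. Neither pairing nor the blinded photograph assessor corrects a non-random choice of lesion.

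**Conclusion.** The concern holds, with medium confidence because a draw may exist in material not seen. As written, 7(f) randomises wavelength in types I–III and leaves laser against control without any described random allocation in every skin type. A reader cannot tell whether the headline result is a randomised comparison.

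The documents do not fix the size or direction of any bias. Under the stated assumptions, the false-positive rate in favour of laser ranges from 2.5% with a random draw to 55% with consistent selection of the worse lesion at correlation 0.5, and the sign can reverse. The largest bias shown, 0.56 points, is well below the 3-point margin in 7(h), so it would not be expected to trigger that rule by itself. This is an inexpensive improvement, and the second hypothesis, on wavelength, is not affected in types I–III.

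**What to change.** State in 7(f) how laser versus control is assigned. Keep the Visit 1 order: select the study lesions and record their baseline scores and photographs. Then, in every participant, draw the control lesion at random from the selected lesions, with the result unknown until that point.

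- **Types I–III, two lesions:** the existing 50:50 draw sets the wavelength for the other lesion.
- **Types I–III, three lesions:** the existing 50:50 draw sets which of the other two gets 532nm and which gets 1064nm.
- **Types IV–VI:** the draw decides which lesion is control and which gets 1064nm.

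Analyse within participant, adjusting for each lesion's baseline score. If a draw is already described in the figure or forms, write it into 7(f).

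The document is dated 22 May 2019, while section 7(e) says "The goal is to conclude the data collection by October 31, 2018". Enrolment status is not given, but some participants may already have been treated. For anyone treated without a draw, report the baseline laser–control difference with its confidence interval, use the baseline-adjusted analysis, and describe laser versus control as non-randomised.

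The cost is one extra draw per participant and a short amendment, or one sentence if a draw is already done. The investigator loses any choice of which selected lesion gets laser. A draw introduced now cannot repair allocation already made.

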- Research will be conducted during [name] clinical time. [name], a UCF Health board-certified physician, will perform the screening of eligible participants. [name] has significant prior experience conducting research, knowledge of the regulations and customs at UCF Health, and works regularly with patients performing laser treatments. Off-label laser treatments currently performed are fractionated CO2 laser for morphea, 1064nm and 532nm laser for sarcoidosis and acne, and 532nm laser for cutaneous lupus among others. Experience has been presented at invited talks/grand rounds. All treatments will be administered by [name].
- All individuals assisting in the research study will be provided a copy of the approved IRB study protocol and given the opportunity to meet with the principal investigator before recruitment begins. The principal investigator, [name], will be responsible for informing all research staff of their research-related duties during a personal meeting or via phone or email. The contact information of the principal investigator and co-principal investigators will be distributed to all research staff and the participants.

- The study will be conducted at the UCF Health Clinic, see section 5 (Setting of the Human Research). Extramural funding will be sought from various organizations or industry.
- The chances of a research related injury are extremely rare. However treatment for research related minor injuries will be made available at no cost by [name] if possible. For injuries that cannot be treated by [name] the participant will be referred elsewhere. Costs associated with this treatment may be billed to the participant's insurance company. Costs not covered by participant's insurance company will be the participant's responsibility.
- The study has been approved by the UCF Health Privacy Officer.

7) Study Design

a) Recruitment Methods

- For this study, we will recruit 25 adult male and female volunteers age 18 years and older. This number was calculated with the University of California San Francisco (UCSF) Clinical and Translational Science Institute Sample Size Calculator with a power of 0.8, effect size of 0.25, and alpha of 0.05.

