- Participants with a diagnosis of cutaneous lupus will be recruited from the UCF Health Clinic during a patient's visit (medical records will not be searched for patients with a diagnosis of cutaneous lupus) and through advertising on the UCF Health website and within the UCF Health clinic. Potential participants also will be identified through email by the Lupus Foundation of Florida to its membership and the Central Florida Society for Dermatology. (See attached "Advertisement").
- [name] and [name] will rely on prior labs, pathology reports, and physical examination to determine if the participant has cutaneous lupus.
- If interested in participating, participants will contact the primary or co-investigator, who will provide instructions on how to enroll in the study.
- The investigator will describe the details of the study and answer any questions the participant may have about the study. Participants will be given an informed consent about the study and the primary investigator's contact information. Those participants who express interest in the study will be required to sign the HIPAA Authorization form (attached), Informed Consent form (attached) to ensure that there is no coercion in the study. Each of these will be signed both by the participant and by [name].

b) Participant Compensation

- The study participants will not be receiving any compensation for their participation in the study.

c) Inclusion and Exclusion Criteria

- For this study, we will recruit approximately 25 male and female volunteers ages 18 and older. All volunteers will be asked to give informed consent and sign a

HIPAA authorization before participation in the experiment. Participants will be screened in person before the research takes place. Participants will be screened and evaluated in the clinic to verify diagnosis through history, physical findings, health records, and previous labs. Participants who fit the diagnosis of cutaneous lupus will be asked whether they wish to participate in the study during the patient visit.

- Inclusion Criteria:
 - Male or female adult 18 years of age or older
 - Ability to rate level of pain
 - Ability to rate visual satisfaction
 - At least 2 active lesions of CLE

- Exclusion Criteria:
 - New or change in systemic medication for cutaneous lupus in past 6 months
 - Allergy to triamcinolone or betamethasone dipropionate cream
 - Pregnancy
 - Currently a prisoner

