 - The Excel V laser system manufactured by Cutera (Brisbane, CA) will be used to administer all laser treatments. This laser has the capability of emitting both 532nm and 1064nm wavelengths.
 - Treatments with the 532nm wavelength will utilize parameters in the following ranges:
 - § Spot size: 1-12mm
 - § Fluence: 5-12 J/cm²
 - § Pulse Duration: 3-15ms
 - § Temperature: 5-10°C
 - Treatments with the 1064nm wavelength will utilize parameters in the following ranges:
 - § Spot size: 1-12mm
 - § Fluence: 10-60 J/cm²
 - § Pulse Duration: 10-60ms
 - § Temperature: 5-10°C
 - Note: If the lesions are ill-defined such as those of ACLE and SCLE then a lesion will be defined as a 2cm² within the involved area.

- Timeline:

Pre-Week 0: Screening Visit

- Screening: participant will be screened for inclusion and exclusion criteria, including urine pregnancy test if necessary.

Week 0: Visit 1

- Baseline lesion assessment, lesion selection, randomization and treatment 1 will occur.

Week 4: Visit 2

- Follow up lesion assessment
- Treatment 2

Week 8: Visit 3

- Final lesion assessment

- Lesion assessment:

Limited CLASI:

The classification of cutaneous lupus will be recorded for each participant.

A “limited” CLASI scoring system will be used, subdivided into an “active” and “damage” components.

The limited active CLASI for a lesion will include the following:

- Erythema (ranging from 0 = absent to 3 = dark red/purple)
- Scale/Hypertrophy (ranging from 0 = absent to 2 = verrucous/ hypertrophic)
- The addition of these scores result in a total limited active CLASI score of the studied lesion, ranging from 0 to 5.

The limited damage CLASI for a lesion will include the following:

- Dyspigmentation (0 = absent or 1 = present)
- Scarring/Atrophy/Panniculitis (ranging from 0 = absent to 2 = severely atrophic scarring or panniculitis).
- The addition of these scores result in a maximum damage score of 3.

The total limited CLASI reflects the sum of both active and damage CLASI, resulting in a score ranging from 0 to 8.

Photographs will be taken of all study lesions during every assessment.

All participants will be evaluated by [name] at baseline and at subsequent visits.

All participants will be evaluated via photograph by [name] at baseline and subsequent visits. [name] will be blinded to the treatment type so as to be an independent observer. He will utilize the “Independent Observer Survey” to document his assessments.

Visual Satisfaction of Appearance:

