Topical corticosteroid associated risks²⁰:

- Atrophy
- Telangiectasias
- Striae
- Perioral dermatitis
- Hypertrichosis
- Folliculitis
- Note: All risks are approximately <5%²¹

9) Potential direct benefits to participants

While there are no guarantees that participants will receive any benefits from their participation in this study, potential benefits include quicker improvement of cutaneous lupus lesions less scarring than standard of care, and topical treatment at no cost for cutaneous lupus for duration of study participation.

10) Provisions to protect the privacy interests of participants

Participants will be seen and treated in the same manner as patients in the UCF Health clinic. In the clinic, efforts are made to protect patients' privacy whenever possible as per HIPAA guidelines.

11) Provisions to maintain the confidentiality of data

Data will be stored in the secure HIPAA-compliant database called REDCap. Unique identifiers will be created using sequential numbers (i.e. 1, 2, 4 etc.).

No data collection instrument in REDCap will contain identifying information

A screening and enrollment log (see attached document “Screening and Enrollment Log”) will be stored in a regulatory binder in a locked drawer in a locked room at UCF Health. Only [name] will have access to this locked drawer.

A subject ID assignment list (see attached document “Subject ID Assignment List”) that links the subject name and contact information with their unique identifier will be stored in a separate folder in locked drawer in a locked room at UCF Health. Only [name] will have access to this locked drawer.

Identifying information such as the “Subject ID Assignment List” will only be accessed by the PI and co-PIs for initial entry. It is possible the identifiable information may be referenced if questionable data are detected during data analysis (e.g.: number out of range, missing data).

The “Screening and Enrollment Log” and the “Subject ID assignment List” will both be disposed of in a HIPAA-compliant shred bin at the completion of the study.

Informed consents and HIPAA authorizations will be stored in locked drawer in a locked room at UCF Health and kept for a minimum of six years after the conclusion of the study (per UCF data retention policies.)

Only de-identified data will be used and exported for analysis.

De-identified data will be stored for a minimum of five years after the conclusion of the study (per UCF data retention policies).

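### The laser coin flip has no described concealment, record or prior locking of lesions, and no random rule chooses the topical-only control lesion

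*Combined protocol and SAP*

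**What the plan says.** Section 7(f), Procedures, describes a randomized study. Every study lesion gets a topical corticosteroid. One lesion gets nothing more and is the control, and up to two others also get laser.

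- **Random step.** The only one described applies to skin types I–III: "50:50 randomization for laser used (determined by coin flip".
- **Types IV–VI.** There is no flip: "Treatment lesion will only be treated with the 1064nm laser".
- **Further lesion, types I–III.** "If the participants have an additional lesion then this will be treated with the laser not used for the treatment lesion". Section 7(c) asks for "At least 2 active lesions of CLE", so a third lesion is optional.
- **Timing.** For Week 0, Visit 1, the timeline in section 7(f) says: "Baseline lesion assessment, lesion selection, randomization and treatment 1 will occur".
- **Records.** The survey form lists the lesion treatment, and photographs are taken at each assessment (section 7(f)). Paper forms are destroyed once entered, and photographs go to the health record (section 7(g)). Section 11 adds: "Data will be stored in the secure HIPAA-compliant database called REDCap".
- **Blinding.** An observer scores photographs without knowing the treatment type (section 7(f)).

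The documents describe no pre-generated list, no concealment, no log of the flip, and no named person or witness for it. They give no rule for choosing the control lesion.

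**The concern.** A coin is a sound randomizer if it is flipped once, after the lesions are fixed, and the result is kept. The plan secures none of these. Section 3 states in advance that the 532 nm laser is expected to do better than the 1064 nm laser, and section 6 has one person give all treatments. Lesion choice is also flexible: where disease is ill-defined, section 7(f) lets a 2 cm² area within the involved skin count as a lesion.

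Two comparisons are exposed. The laser-against-laser hypothesis depends on the flip. Laser plus topical against topical alone depends on which lesion becomes the control, and no chance mechanism is described for that. If more responsive lesions tend to become laser lesions, the contrast is biased at baseline. A blinded reading of the photographs protects the scoring but cannot undo the selection.

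**Working it through.** **1. The plan's own figure.** Section 7(a) gives 25 participants from "power of 0.8, effect size of 0.25, and alpha of 0.05". It gives no number for those who are flipped. If 0.25 is a standardized paired difference, n = (1.960 + 0.842)² / 0.25² = 7.849 / 0.0625 = 125.6, so 126. To reach 25 with a raw difference of 0.25, the SD of the difference must be 0.25 × √25 / 2.802 = 0.446, which is not stated. The figure is therefore not reproduced, because inputs are missing. Nothing below depends on it except 25 as the upper limit.

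**2. What chance decides, by participant.**

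| Participant | Which lesion is control | Which laser |
|---|---|---|
| Types I–III, two lesions | no rule described | coin flip |
| Types I–III, three lesions | no rule described | coin flip for one laser lesion, the other laser for the second |
| Types IV–VI | no rule described | 1064 nm by rule |

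For types IV–VI no described element is random.

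**3. What the described records would show.**

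| Event | Trace |
|---|---|
| Treatment given to each lesion | yes, survey form and then REDCap |
| Flip repeated or overridden | none described |
| Lesions fixed before the flip | listed order of steps only; no locking step or time stamp described |
| Control lesion chosen with treatment in mind | none described |

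**4. Size of imbalance (secondary).** Let n be the number of type I–III participants. It is not stated, so a range is shown. Assume first that each has one laser lesion. The number given 532 nm is then Binomial(n, 0.5), and both tails are added.

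| n | Split or worse | Probability |
|---|---|---|
| 8 | 6:2 | 2 × (28 + 8 + 1) / 256 = 0.289 |
| 12 | 8:4 | 2 × (495 + 220 + 66 + 12 + 1) / 4096 = 0.388 |
| 12 | 9:3 | 2 × (220 + 66 + 12 + 1) / 4096 = 0.146 |
| 12 | 10:2 | 2 × (66 + 12 + 1) / 4096 = 0.039 |
| 20 | 14:6 | 0.115 |
| 25 | 17:8 | 0.108 |

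**5. Cost of imbalance.** The efficiency of a split a:b relative to an equal one is 4ab/n². Since E[X(n − X)] = n(n − 1)/4, expected efficiency is 1 − 1/n. The loss is 12.5% at n=8, 8.3% at n=12, 5% at n=20 and 4% at n=25. At n=12 the standard error rises by the factor √[(1/a + 1/b) / (1/3)]: 1.06 for 8:4, 1.15 for 9:3 and 1.34 for 10:2.

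**6. Effect of the further-lesion rule.** At n=12, suppose m participants have a third lesion and so contribute one lesion to each laser. The chance that lesion counts differ by 2:1 or more is:

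- m=0: 0.388
- m=4: a count of 11:5 or worse, 2 × (1 + 8) / 256 = 0.070
- m=6: a count of 12:6, 2 / 64 = 0.031
- m=8 or more: 0, since the worst count at m=8 is 12:8

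**The case against.** The strongest reply is that a fair coin is valid and less predictable than fixed small blocks, whose last entries can be inferred when one person gives all treatments. This stands. A reader might infer that the lack of blocking itself opens the door to selection. It does not: the opening is the missing concealment and documentation.

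A reader might also infer that the laser groups will be badly unequal, with about a dozen participants flipped. The documents give no skin-type breakdown, so 12 is only an assumption. The average loss is small, unequal numbers do not bias the comparison, and the further-lesion rule can remove most or all of the imbalance. That rule does not remove the selection concern, because in three-lesion participants the flip still decides which lesion gets which laser. Nor would balance among types I–III equalize the lasers overall, since all of types IV–VI receive 1064 nm.

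Two further replies are fair. The Visit 1 list already puts lesion selection before randomization, and baseline photographs are planned. That is the right order, but no described step enforces or dates it. The survey form and the enrollment log are attachments not available here and might record the flip. The text that is available lists only the lesion treatment.

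Finally, the word randomization at Visit 1 could be meant to cover the choice of control lesion. Section 7(f) spells out a random rule for the laser only, so that reading needs to be written down.

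**Conclusion.** The point holds as a gap in concealment and documentation, together with an unstated rule for the control lesion. It is a worthwhile improvement rather than a fatal flaw. The documents do not show that any allocation was or would be manipulated, and do not say who flips the coin. The treatment of each lesion is recorded, so it would be too strong to say that nothing can be audited. What cannot be verified from the described records is that the flip was made once, after the lesions were fixed, and that the control lesion was not chosen with its treatment in mind. The control-lesion gap applies to all 25 participants, the flip only to types I–III. Any bias cannot be sized from the documents.

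The precision cost is minor: an expected loss of 1/n, or about 8% if n=12. This assumes one laser lesion per type I–III participant and falls towards zero as third lesions become common.

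**What to change.** Replace the coin flip with a computer-generated list prepared by the statistician already named in section 7(g) and held in REDCap.

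- Release each entry, with a time stamp, only after the study lesions have been numbered, scored and photographed and the baseline record has been saved.
- Each entry should state which numbered lesion is the control and, for types I–III, which laser goes to which lesion. It needs a version for two lesions and one for three.
- Use separate lists for types I–III and IV–VI, so that the control lesion is randomized in both.
- Blocking is optional and serves precision only. If blocks are used, vary their size and hide it from the treating team.

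The cost is a short set-up by the statistician in a database already in use. The change adds no visit and leaves the treatments as they are.
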